The “5+2” doses must be given within approximately 1 year (i.e., the start of one course to start of the second course within 12 months  $\pm 1$  month) and given to treat the same disease episode with which the subject is enrolling. Additional doses and courses of BCG are permitted as part of “adequate BCG.” All subjects must have disease for which the investigator would not treat with additional BCG treatment at this time.

Three cohorts of subjects will enroll:

- Cohort 1: Subjects with CIS with or without associated papillary disease whose disease is determined to be refractory or relapsed within 6 months of the last dose of adequate BCG treatment.
- Cohort 2: Subjects with CIS with or without associated papillary disease whose disease is determined to be refractory or relapsed more than 6 months but within 11 months of the last dose of adequate BCG treatment.
- Cohort 3: Subjects with high-grade Ta or any grade T1 papillary disease (without CIS) whose disease is determined to be refractory or relapsed within 6 months of the last dose of adequate BCG treatment.

For eligibility and cohort assignment, 6 months is defined as 30 weeks, i.e., 26 weeks (6 months) plus an additional 4 weeks to accommodate scheduling variations and for diagnostic work-up, and 11 months is defined as 50 weeks, i.e., 48 weeks (11 months) plus an additional 2 weeks to accommodate scheduling variations and for diagnostic work-up.

Of the 134 subjects  $\geq 77$  subjects will accrue to Cohort 1. Up to 57 additional subjects in total may accrue to Cohorts 2 and 3. This is an outpatient study. All treatments may be administered in the study clinic. Each subject’s study course consists of a Screening Period, a 12-week Induction Phase, a Maintenance Phase and a Post-Treatment Evaluation. Following the 12-week Induction Phase, subjects will be evaluated for disease status as described in **Section 14**. Subjects without a treatment failure as specifically defined in **Section 14.2** or other criteria necessitating discontinuation of study treatment (see **Section 11.3**) will begin the Maintenance Phase. Subjects will receive treatment for up to 2 years in total if they are tolerating treatment and do not meet the definition of protocol-defined treatment failure or other criteria for study discontinuation. Following the Post-Treatment Evaluation, additional subject data will be collected as needed for the evaluation of the Secondary Endpoints.

The treatments are as follows:

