## 12 TREATMENT

### 12.1 Study Drug Administration

Subjects will receive study drug treatments twice weekly (BIW) for 6 weeks and once weekly for 6 weeks during the Induction Phase, and then enter the Maintenance Phase, if eligible ([Table 5](#)).

**Table 5:** Treatments

Study Phase	Treatment Regimen
Induction Phase (Weeks 1-12)	One intravesical dose of Vicinium 30 mg in 50 mL of saline instilled twice weekly (BIW) for 6 weeks followed by once weekly for 6 weeks, for a total of 12 weeks. The twice weekly doses are to be administered at least 48 hours apart (and no more than 2 doses may be administered within a calendar week, i.e., within a Sunday through Saturday period.) As an example, while a Monday/Thursday or Tuesday/Friday would be optimal, a Monday/Wednesday or a Tuesday/Thursday dosing schedule could be used. There will be a total of 18 doses over the 12-week period of the Induction Phase.
Maintenance Phase (up to Week 104)	One intravesical dose of Vicinium 30 mg in 50 mL saline instilled once every other week, for up to 24 months (Week 104) from the start of the Induction Phase.

To reduce urine flow during the instillation and dwell of Vicinium in the bladder, subjects will be asked to refrain from drinking any liquids beginning 2 hours prior to study drug instillation through completion of the 2-hour time period during which drug is held in the bladder. Immediately prior to bladder catheter insertion, subjects will empty their bladder. Appropriate study personnel will then insert a catheter into the bladder, and the bladder will be drained.

An appropriate local anesthetic and sterile lubricant may be used at the time of catheterization. In addition, an antibiotic may be given at the discretion of the Investigator. The use of any medications must be recorded on the subject CRF.

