3.3.2. Examination of Subject Subsets

Analyses of the mITT population will be summarized by cohort at study entry and an overall CIS group.

To assess consistency of efficacy endpoints, the primary and secondary efficacy analyses will be performed for the following subgroups:

- Age ($<75, \geq 75$)
- Gender (Male, Female)
- Region (US, Canada)
- Race (White, Black/African American, Asian, Other)
- Number of prior BCG therapies ($\leq 2, > 2$)
- Number of prior BCG instillations ($\leq 9, \geq 10$)

In each subgroup, CR rate and the associated 95% CI will be calculated, and median values and associated 95% CIs will be calculated for all time-to-event endpoints for the appropriate cohort (EFS, cystectomy-free days, time to disease recurrence, time to progression, PFS, and OS). Results will be displayed in forest plots and Kaplan-Meier curves when indicated.

Adverse events will also be analyzed by subgroup (adverse events, serious adverse events, treatment-related adverse events treatment-related, serious adverse events, and Grade 3 or higher adverse events).

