3.3.7. Definitions and Terminology

Adverse Event

An adverse event (AE) is defined as any unfavorable and unintended sign (including an abnormal laboratory finding), symptom or disease temporally associated with the use of a medical treatment or procedure regardless of whether it is considered related to the medical treatment or procedure (attribution of unrelated, unlikely, possible, probable, or definite).

Any medical condition that is present at the time the subject is screened, but does not deteriorate, should not be reported as an AE. However, if it deteriorates at any time during the study it should be recorded as an AE. Hospitalization for elective treatment of a preexisting condition that did not worsen from baseline is not considered an AE or serious AE (SAE).

The descriptions and grading scales found in the revised National Cancer Institute Common Terminology Criteria for Adverse Events (NCI-CTCAE) version 4.03 will be utilized for AE reporting.

Serious Adverse Event

A serious adverse event is any AE that is fatal, life-threatening, requires or prolongs hospital stay, results in persistent or significant disability or incapacity, results in a congenital anomaly or birth defect, or is an otherwise important medical event.

Treatment-emergent AE

Treatment-emergent AEs (TEAEs) are all AEs occurring on or after the date of first dose of study drug through 30 days post the last dose of study drug.

Baseline Value

For purposes of analysis, the baseline value is defined as the last value obtained prior to the first dose of Vicinium.

Study Drug

For the purposes of this study, the term study drug refers to Vicinium.

Day 1 (Baseline)

Day 1 is the day that the first dose of Vicinium is received.

Age

The age of a subject is defined as (Date of Informed Consent – Date of Birth + 1)/365.25.

Study Day

Study Day is defined relative to Baseline (Day 1). Thus, the study day of an event is calculated as:

$$\text{Study Day} = \text{event date} - \text{date of Day 1} + 1.$$

Change from Baseline

Change from baseline for a given endpoint is defined as the Study Day X value minus the Baseline Value.

Cohort 1 Subjects

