5. STATISTICAL METHODS

Descriptive statistical methods will be used to summarize the data from this study, with hypothesis testing performed for the primary and other selected efficacy endpoints. Unless stated otherwise, the term “descriptive statistics” refers to number of subjects (n), mean, median, standard deviation (SD), minimum, and maximum for continuous data and frequencies and percentages for categorical data.

All data collected during the study will be included in data listings. Unless otherwise noted, the data will be sorted first by subject number and then by phase (induction, maintenance), cycle/visit, and date.

Unless otherwise specified, all statistical testing will be two-sided, and will be performed using a significance (alpha) level of 0.05.

The statistical analyses will be conducted with the SAS® software package version 9.2 or higher. All analyses will be subject to formal verification procedures. Specifically, results will be verified utilizing independent programming prior to issuance of the draft statistical report. All documents will be verified by the lead statistician to ensure accuracy and consistency of analyses.

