5.3. SAFETY

5.3.1. Adverse Events

Adverse events will be mapped to a Medical Dictionary for Regulatory Activities (MedDRA) version 18.0 or higher preferred term and system organ classification. The severity of all AEs will be assessed

by the investigator according to the protocol and the CTCAE v 4.03 criteria. If a subject experiences multiple events that map to a single preferred term, the greatest severity grade and strongest investigator assessment of relation to study medication will be assigned to the preferred term for the appropriate summaries. Should an event have a missing severity or relationship, it will be classified as having the highest severity and/or strongest relationship for the purposes of summary analyses. For presentation in the data listings, the missing values will be noted. The occurrence of TEAEs will be summarized by phase (induction vs maintenance) using preferred terms, system organ classifications, and severity. Separate summaries of treatment-emergent SAEs, TEAEs related to Vicinium, TEAEs leading to discontinuation of study or study drug, serious TEAEs, and Grade 3 or higher TEAEs will be generated. All AEs reported will be listed for individual subjects showing both verbatim and preferred terms. Missing onset dates will be imputed as previously outlined in Section 3.3.5 as required to determine treatment-emergent events.

Summaries of TEAEs, TEAEs related to Vicinium, Serious TEAEs, and Grade 3 or higher TEAEs will also be presented by each subgroup.

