- Presentation of sample sizes: Summary modules should indicate, in one way or another, the number of subjects actually contributing to the summary statistics presented in any given summary module. As mentioned above, this may be less than the number of subjects in the analysis population.
 - ◆ In the quantitative modules describing continuous variables (and thus presenting sample size, means, and standard deviations), the sample size should be the number of non-missing observations
 - ◆ For categorical variables that are presented in frequency tables, the module should present the total count in addition to the count in each category. Percentages should be calculated using this total as the denominator, and the percentage corresponding to the sum itself (that is, 100%) should be presented to indicate clearly to a reviewer the method of calculation.
- Sorting: Listings will be sorted first by subject number and then by phase (induction, maintenance), visit, and date, if applicable. If a listing is sorted in a different manner, a footnote will indicate as such.
- General formatting rules: Rounding for all variables will occur only as the last step, immediately prior to presentation in listings, tables, and figures. No intermediate rounding will be performed on derived variables. The standard rounding practice of rounding numbers ending in 0-4 down and numbers ending in 5-9 up will be employed.
- The presentation of numerical values will adhere to the following guidelines:
 - ◆ Raw measurements will be reported to the number of significant digits as captured electronically or on the CRFs.
 - ◆ Standard deviations will be reported to one decimal place beyond the number of decimal places the original parameter is presented.
 - ◆ Means will be reported to the same number of significant digits as the parameter.
 - ◆ Calculated percentages will be reported with no decimals.

- Dates will be formatted as DDMMYYYY. Partial dates will be presented on data listings as recorded on CRFs.
 - ◆ Time will be presented according to the 24-hour clock (HHMM).

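### Subgroup adverse-event tables carry no stated phase split or allowance for time at risk, so a subgroup that responds better can show more events with no difference in toxicity

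*SAP*

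**What the plan says.** SAP Section 3.3.2 names six subgroup factors: age, gender, region, race, number of prior BCG therapies and number of prior BCG instillations. It states that "Adverse events will also be analyzed by subgroup". Section 5.3.1 adds: "Summaries of TEAEs, TEAEs related to Vicinium, Serious TEAEs, and Grade 3 or higher TEAEs will also be presented by each subgroup". Section 12 lists the resulting tables: six factors for each of four event types, or 24 tables.

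The measure comes from the SAP's general rules. Section 5 prescribes "frequencies and percentages for categorical data", and the programming conventions in Section 9 say "Percentages should be calculated using this total as the denominator", the total being a count of subjects. The treatment-emergent definition in Section 3.3.7 covers "all AEs occurring on or after the date of first dose of study drug through 30 days post the last dose of study drug". The SAP names no rate per unit of time at risk and no time-to-first-event analysis for adverse events. Section 5.3.2 summarises exposure descriptively and mentions no subgroup split.

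Section 5.3.1 does say that the occurrence of TEAEs will be summarised by phase, induction versus maintenance. The sentence on subgroups stands in a separate paragraph and does not repeat this.

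On time on drug, the protocol synopsis says: "Subjects will receive treatment for up to 2 years in total if they are tolerating treatment and do not meet the definition". The rest of that sentence refers to treatment failure and other discontinuation criteria. Protocol Section 10.4 admits to maintenance only subjects without treatment failure. Section 11.3 and Table 7 in Section 14.4 end treatment at a later failure.

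**The concern.** Treatment failure ends dosing, and the TEAE window closes 30 days after the last dose, so a subject's chance to record an event depends in large part on the efficacy outcome. SAP Section 3.3.2 uses the same six factors for efficacy and for adverse events. If one level of a factor responds better, its members stay on drug longer and have more time to record a first event. A percentage of subjects takes no account of that time.

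A reader could then take a difference in exposure for a difference in tolerability. The converse also matters: a subgroup that fails early can look well tolerated because it was observed for less time. The efficacy endpoints in these subgroups get time-to-event estimates with confidence intervals, while the adverse events in the same subgroups get nothing comparable.

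**Working it through.** The documents state no figure for this point, so there is none to reproduce.

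**Time at risk and doses.** Inputs: 12-week induction ("There will be a total of 18 doses over the 12-week period of the Induction Phase", Protocol Section 12.1), treatment to week 104 at most with maintenance dosing every other week (Protocol Section 10), and the 30-day TEAE tail (SAP Section 3.3.7).

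- Failure at the post-induction evaluation: (84 + 30)/7 = 16.3 weeks, 18 doses. If the last dose falls on the SAP's target day 78, (78 + 30)/7 = 15.4 weeks.
- Completer: (728 + 30)/7 = 108.3 weeks, 18 + 92/2 = 64 doses if none is missed.
- Ratios: 108.3/16.3 = 6.6 in time, 64/18 = 3.6 in doses.
- A subject who stops after one dose is at risk for about 31/7 = 4.4 weeks, so 16 weeks is not the true minimum.

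**Effect on the percentage.** Assumptions not in the documents:

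- Response at the post-induction evaluation (c) is 30% in one subgroup and 50% in the other. The 30% borrows the plan's 12-month response assumption only as an anchor.
- 75% of responders are kept at each later 13-week visit (range 60% to 90%).
- 10% of subjects have an event by week 16.3 (range 5% to 20%).
- Both subgroups have the same hazard.

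Responders stop at week 26, 39, 52, 65, 78, 91 or 104, each plus 30 days, with weights 0.250, 0.188, 0.141, 0.105, 0.079, 0.059 and 0.178. Their mean time at risk is 62.3 weeks. The subgroup mean is (1 − c) × 16.3 + c × 62.3, which gives 30.1 weeks at c = 30% and 39.3 weeks at c = 50%.

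The percentage with at least one event is (1 − c) × 10% + c × R, where R is the weighted mean over responders of 1 − exp(−cumulative hazard).

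| Hazard shape | R | c = 30% | c = 50% | Gap (points) |
|---|---|---|---|---|
| Constant per week: −ln(0.9)/16.3 = 0.00647 | 32.1% | 16.6% | 21.0% | 4.4 |
| Proportional to scheduled dosing: 1.5 per week to week 12, then 0.5 | 19.9% | 13.0% | 14.9% | 2.0 |
| Only in the first 16.3 weeks | 10.0% | 10.0% | 10.0% | 0 |

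As an example, constant hazard at c = 30% gives 0.7 × 10% + 0.3 × 32.1% = 16.6%. The 2.0 comes from unrounded values (12.96% and 14.93%).

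Range under constant hazard:

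- Retention 60%: 14.9% vs 18.2%. Retention 90%: 19.4% vs 25.6%.
- 5% with an event by week 16.3: 8.8% vs 11.3%. 20%: 30.3% vs 37.2%.

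**Candidate remedies** (30% vs 50% response, 10% by week 16.3).

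- *One whole-period rate*, first events per 100 subject-weeks: constant hazard 0.647 vs 0.647 (ratio 1.00), dosing-rate hazard 0.483 vs 0.433 (0.90), early-only hazard 0.359 vs 0.276 (0.77). It is neutral only under constant hazard. Otherwise it favours the better-responding subgroup.
- *Percentage over a common early window*, to week 16.3: 10% vs 10% under all three shapes.
- *Induction cut at different times.* Suppose responders are counted to week 12 but failures keep their 30-day tail to week 16.3. Under constant hazard a responder's percentage is 1 − exp(−0.00647 × 12) = 7.5%. The subgroups then show 0.7 × 10 + 0.3 × 7.5 = 9.2% and 0.5 × 10 + 0.5 × 7.5 = 8.7%, a reverse gap of about 0.5 points. The cut should therefore be the same for everyone.

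**The case against.** **The plan already has a phase split.** It does, in the same section, and it separates the common 12-week schedule from response-dependent maintenance. The missing phase in the subgroup table titles is weak evidence, because the overall TEAE table title in Section 12 names no phase either, although the text promises one. So a reader might infer that the SAP ignores phase altogether; it does not. What stands is that the SAP never says the split reaches the subgroup tables. Even where it does, time within maintenance still depends on response.

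**No comparison is planned.** Correct. The SAP says that events are analysed and presented by subgroup. Section 5 keeps hypothesis testing for efficacy endpoints, and the stated aim of assessing consistency is attached to efficacy. The documents do not support saying that subgroups are formally compared on safety. The weaker point remains: percentages tabulated by subgroup will be compared by readers.

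**Response alone does not set exposure.** Correct. Protocol Section 11.3 also ends dosing for toxicity, withdrawal of consent, non-compliance and intercurrent illness. A subgroup that tolerates the drug poorly can lose time at risk for that reason.

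**The bias may be absent.** If events cluster in induction, when scheduled dosing is three times as frequent, the gap is zero. A reader might infer that any subgroup with a higher response rate must look less safe. That follows only if risk continues into maintenance, and the documents do not settle this.

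**The gap is small against noise.** With 134 subjects split 67/67, the 95% half-width for a difference in percentages is 1.96 × √(2 × 0.1 × 0.9/67) = 10 points at an event rate of 10%, and 16 points at 30%. The illustrated gaps are smaller. This limits the severity, but it does not make a systematic distortion harmless in tables meant to be read descriptively.

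**Conclusion.** The point holds in a limited form. As written, the 24 subgroup adverse-event tables are percentages of subjects with no stated phase split and no allowance for time at risk, while time at risk runs from about 16 weeks (post-induction failure) to about 108 weeks (completer), largely according to response. A better-responding subgroup can therefore show more events at equal toxicity.

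The size is about 4 points under constant hazard, about 2 if risk follows the dosing rate, and zero if events occur only early. This assumes 30% against 50% response, 75% retention per visit and 10% with an event by week 16.3. Across the ranges shown, the constant-hazard gap runs from 2.5 points (5% base rate) to 6.9 points (20% base rate). Subgroup response rates, retention and event rates are all assumed.

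No efficacy conclusion and no planned test depends on this. Severity is minor, and the change is a cheap improvement.

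**What to change.** In SAP Sections 3.3.2 and 5.3.1, and in the titles of the Section 12 subgroup tables:

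1. State that every subgroup adverse-event table is split into induction and maintenance. Define one cut that is the same for all subjects, and say to which phase events in the 30 days after the last induction dose belong.
2. Within maintenance, give either subjects with a first event per 100 subject-months at risk, with a 95% confidence interval, or Kaplan-Meier time to first event.
3. Show time on drug by subgroup beside these tables. Section 12 now lists time-on-treatment plots overall and by disease cohort, not by the six factors.
4. Do not rely on one whole-period rate per unit of time at risk.

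The cost is SAP wording, retitled tables and added columns. Study drug administration and adverse-event dates are already collected, so no new data are needed. The drawback is that maintenance subgroups will be small and their intervals wide, which should be stated in a footnote.

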5.3.2. Study Drug Exposure and Concomitant Medications

Exposure to study drug will be summarized with quantitative descriptive statistics.

Previous and concomitant medications will be coded using the World Health Organization (WHO) dictionary (Version: Q4 March 2015). Concomitant medications will be summarized by frequency of drug classification and generic drug name. Previous and concomitant medications will be presented in a data listing

5.3.3. Clinical Laboratory Assessments

Descriptive summaries of all quantitative clinical laboratory results will be presented by phase and visit, as appropriate. Laboratory abnormalities will be graded according to the NCI CTCAE version 4.03 grading system (http://evs.nci.nih.gov/ftp1/CTCAE/CTCAE_4.03_2010-06-14_QuickReference_5x7.pdf). The number and percentage of subjects experiencing treatment-emergent graded laboratory toxicities will be summarized. A laboratory abnormality is considered a treatment-emergent toxicity if it is an increase of 1 grade or more from the baseline toxicity value. Laboratory toxicity shifts from baseline to worst post-treatment toxicity will also be presented.

A spaghetti plot of clinical assessment by visit for subjects with a treatment emergent Grade 3 or higher lab abnormality. In addition scatter plots of lab values versus baseline will be produced for select labs by visit.

All clinical laboratory toxicities that occurred before the initiation of study drug will be excluded from the tables but will be included in the listings.

5.3.4. Other Safety Analyses

Descriptive summaries of vital signs and their change from baseline will be presented by visit. The following values of vital signs will be considered potentially significant:

- Diastolic blood pressure
 - ≤ 55 mmHg and/or decrease of ≥ 20 mmHg from baseline

- ≥ 90 mmHg and/or increase of ≥ 30 mmHg from baseline
- Systolic blood pressure
 - ≤ 90 mmHg and/or decrease of ≥ 30 mmHg from baseline
 - ≥ 160 mmHg and/or increase of ≥ 40 mmHg from baseline
- Pulse
 - ≤ 50 bpm and/or decrease of ≥ 30 bpm from baseline
 - ≥ 120 bpm and/or increase of ≥ 30 bpm from baseline
- Temperature $> 38.3^{\circ}\text{C}$

The number and percentage of subjects with potentially significant vital signs will be summarized by visit.

Results from the triplicate 12-lead ECGs will be averaged and summarized by visit. Corrected QT values will be calculated using the Fridericia and Bazett corrections. The number and percentage of subjects with QTcF values > 470 msec for females and > 450 msec for males will be summarized by visit.

Medical history, physical examination findings, and pregnancy test results will be presented in the data listings.

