8. A QTc interval of >470 msec by the Fridericia formula (QTcF), at the Screening ECG. If the subject's QTcF is >470 msec on the initial ECG, a total of 3 ECGs should be obtained at least 3 minutes apart and all within 30 minutes. The average of the 3 QTcF's will be used to determine eligibility. Known or suspected causes of prolonged QTc can be treated (e.g., hypocalcemia, hypokalemia, hypomagnesemia) and the ECGs may be repeated. If the subject initiates treatment with a drug known to prolong the QTc during the Screening period after the initial Screening ECGs were obtained, the Screening ECGs must be repeated once the new drug has reached steady state to ensure the average QTcF remains ≤470 msec. For subject's whose heart rate is <60 bpm, the Bazett correction formula (QTcB) may be used.
9. Subjects who, in the opinion of the Investigator, cannot tolerate intravesical administration or intravesical surgical manipulation (cystoscopy, biopsy) due to the presence of serious comorbid condition(s) (e.g., uncontrolled cardiac or respiratory disorders).
10. Local or severe allergy to any components of the drug regimen.

**Investigational product, dosage and mode of administration:** Vicinium™ 30 mg in 50 mL of saline administered intravesically

**Duration of treatment:** Up to 24 months

**Reference therapy, dosage and mode of administration:** None

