 White-light cystoscopy. Any subject who undergoes fluorescence cystoscopy for bladder biopsy/TURBT during the screening period must continue having this modality for all subsequent biopsies (however, white-light cystoscopy will suffice for all assessments if a biopsy is not required ([Section 14](#))).

 Directed biopsies of all areas suspicious for disease. Random biopsies are required if cystoscopy is negative and urine cytology is positive or there are two suspicious cytology results ([Section 14](#))

 CT urogram or MRI urogram. If intravenous contrast is contraindicated, retrograde ureteropyelography, or CT or MRI without intravenous contrast may be performed. Required during Screening for all subjects with T1 disease. Required for all other subjects if not previously performed within 13 weeks before the start of dosing.

 Single tracing only at Screening unless QTc is prolonged ([Section 16.4](#)); thereafter, triplicate ECGs are to be performed.

 Update medication history.

 Performed every 4 weeks (i.e., week 4, week 8, week 12, etc.) while on treatment in females of childbearing potential only.

 Cytology sample pre-dose on Day 1. Note: Chemistry, hematology (CBC and differential), urinalysis and physical examination need to be performed pre-dose Day 1 only if not performed in the Baseline Period ( $\leq 7$  days before the first dose of study medication).

 Evaluation performed pre-dose and post-dose prior to leaving the clinic.

 Evaluation performed pre-dose. Concomitant medications required post-dose only if additional medications (not including Vicinium) were administered during or after the start of the instillation.

 Weeks 2-5: Chemistry and hematology (CBC and differential) performed once weekly ([Section 10.3.2](#)). Week 4: Targeted physical examination. Week 6: Urinalysis performed pre-dose at the second dose of the week; Hematology (CBC and differential) and chemistry ([Section 10.3.3](#)). Weeks 7-11: Chemistry and hematology (CBC and differential) performed once weekly ([Section 10.3.4](#)). Week 8: Targeted physical examination. Week 12: Urinalysis performed pre-dose. Hematology (CBC and differential), chemistry([Section 10.3.5](#)). Targeted physical examination, and triplicate ECG performed post-dose prior to leaving the clinic.

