8. A QTc interval of  $>470$  msec by the Fridericia formula (QTcF), at the Screening ECG. If the subject's QTcF is  $>470$  msec on the initial ECG, a total of 3 ECGs should be obtained at least 3 minutes apart and all within 30 minutes. The average of the 3 QTcF's will be used to determine eligibility. Known or suspected causes of prolonged QTc can be treated (e.g., hypocalcemia, hypokalemia, hypomagnesemia) and the ECGs may be repeated. If the subject initiates treatment with a drug known to prolong the QTc during the Screening period after the initial

Screening ECGs were obtained, the Screening ECGs must be repeated once the new drug has reached steady state to ensure the average QTcF remains  $\leq$ 470 msec. For subject's whose heart rate is  $<60$  bpm, the Bazett correction formula (QTcB) may be used.

9. Subjects who, in the opinion of the Investigator, cannot tolerate intravesical administration or intravesical surgical manipulation (cystoscopy, biopsy) due to the presence of serious comorbid condition(s) (e.g., uncontrolled cardiac or respiratory disorders).
10. Local or severe allergy to any components of the drug regimen.

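### SAP 5.3.4 counts QTcF above 450 msec (men) and 470 msec (women) without reference to baseline, so pre-existing values are not separated from new prolongation

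*SAP*

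**What the plan says.** **Entry.** Exclusion criterion 8 (Protocol Synopsis and 11.2, repeated in 16.4) sets one limit for both sexes: "A QTc interval of >470 msec by the Fridericia formula (QTcF), at the Screening ECG". It adds an exception: "For subject's whose heart rate is <60 bpm, the Bazett correction formula (QTcB) may be used".

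**ECG times.** Footnote 5 of Protocol Table 3 describes the pre-dose ECG: "Single tracing only at Screening unless QTc is prolonged". Triplicates follow after the Week 12 dose and at the Post-Treatment evaluation, 30 to 37 days after dosing ends (Protocol 10.3.5, 10.6).

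**Analysis.** SAP 5.3.4 plans two ECG outputs. The first is a by-visit summary: "Results from the triplicate 12-lead ECGs will be averaged and summarized by visit". The second is the threshold count: "The number and percentage of subjects with QTcF values > 470 msec for females and > 450 msec for males will be summarized by visit". The final outputs contain one ECG table (14.3.6) and one listing of individual ECGs (16.2.8.4).

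**Other safety data.** The same SAP section says of vital signs: "Descriptive summaries of vital signs and their change from baseline will be presented by visit". SAP 5.3.3 ties laboratory findings to the starting grade: "A laboratory abnormality is considered a treatment-emergent toxicity if it is an increase of 1 grade or more from the baseline toxicity value". It also plans baseline-to-worst shifts and plots of later values against baseline for selected tests.

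**The concern.** The reporting flag for men lies inside the range in which men may enroll, and the count ignores where each subject started. A count of men above 450 msec at Week 12 therefore mixes men who crossed the limit after dosing with men who were already above it.

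The count also misses movement below the limit. A man who goes from 390 to 449 msec has risen by 59 msec and is not counted, while a man who stays at 455 msec is counted each time. Only Listing 16.2.8.4 shows the first man's rise as his own change.

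At stake is how the QT part of a single-arm safety report reads. Unchanged pre-existing values could be taken for prolongation on study, and individual rises could go untabulated. SAP 3.3.7 defines baseline value and change from baseline in general terms, but neither SAP 5.3.4 nor the title of Table 14.3.6 applies them to ECGs.

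**Working it through.** The plan states no figure on this point, so there is none to reproduce. The check compares the limits, applies the SAP's QT formulas, and illustrates the size under stated assumptions.

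**1. Gap between entry limit and flag**
- Men: 470 − 450 = 20 msec. Any man admitted above 450 and up to 470 msec is above his flag before the first dose.
- Women: 470 − 470 = 0 msec, apart from the low-heart-rate exception in step 2.

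**2. Subjects admitted on QTcB**

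SAP 3.3.7 gives QTcF = QT / RR^(1/3) and QTcB = QT / RR^(1/2), so QTcF = QTcB × RR^(1/6), with RR = 60 / heart rate. I take the 470 msec limit to apply to QTcB when that formula replaces QTcF. For a subject admitted at exactly QTcB = 470 msec:

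| Heart rate (bpm) | RR (s) | QTcF (msec) |
|---|---|---|
| 59 | 1.017 | 471.3 |
| 55 | 1.091 | 476.9 |
| 50 | 1.200 | 484.5 |
| 45 | 1.333 | 493.1 |

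Such a subject, of either sex, is eligible and already above the SAP flag, which uses QTcF.

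**3. How many men might start above 450 msec**

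The documents give no QTc distribution. Assume male QTcF at entry is normal with mean m and SD s, truncated at 470. The share already above 450 is [Φ((470 − m)/s) − Φ((450 − m)/s)] / Φ((470 − m)/s).

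| Assumed mean (msec) | SD 15 | SD 20 | SD 25 |
|---|---|---|---|
| 405 | 0.1% | 1.2% | 3.1% |
| 415 | 1.0% | 3.7% | 6.8% |
| 425 | 4.7% | 9.5% | 12.7% |

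Worked cell, m = 415 and s = 20: (Φ(2.75) − Φ(1.75)) / Φ(2.75) = (0.9970 − 0.9599) / 0.9970 = 3.7%.

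**4. What the by-visit count can and cannot show**

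Keep m = 415 and s = 20, and add the same shift to every man after dosing:

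| Shift (msec) | Above 450 at baseline | Above 450 after dosing |
|---|---|---|
| 0 | 3.7% | 3.7% |
| +10 | 3.7% | 10.3% |
| +20 | 3.7% | 22.4% |

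With no shift and stable values, the planned count is 3.7% and a count of newly exceeded limits is 0%. With a uniform shift, the by-visit percentages do move, provided the baseline share is shown beside them.

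**5. Whether the table supplies that comparison**
- The averaging sentence in SAP 5.3.4 refers to triplicates. Screening is usually one tracing, and the section does not say whether it is tabulated as a visit.
- All enrolled subjects should have a Screening ECG, but only those who reach Week 12 have one there. Unpaired percentages at the two times describe different groups.
- SAP 3.3.8 assigns Post-Treatment visits to windows by date. Read as written, a last dose on Day 78 puts that ECG at Days 108 to 115 (78 + 30 to 78 + 37), in Maintenance Month 1 (after Day 91, to Day 121). A last dose in Week 104 (Days 722 to 728) puts it at Days 752 to 765, in Maintenance Month 21 (after Day 698, to Day 773). Off-drug ECGs would then be scattered by stopping time.

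**The case against.** A reader might infer more than the documents support, in three ways.

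- **That the summary cannot show a drug effect.** SAP section 5 defines descriptive statistics as n, mean, median, SD, minimum and maximum. A general rise in QTcF would move the by-visit mean and median even if nobody crossed a limit. SAP 3.3.8 presents visits by nominal CRF visit, and nothing excludes Screening. If it is shown, the pre-dose share above 450 msec stands beside the later ones. This objection stands. What remains is that no within-subject change and no count of newly exceeded limits is planned.
- **That 450 against 470 msec is a contradiction.** An entry limit and a reporting flag serve different purposes, and a lower flag for men is simply more sensitive. This also stands. The weakness is that the count is not tied to baseline.
- **That QTc is the trial's only cardiac pharmacodynamic readout.** The protocol treats ECGs as safety monitoring, no endpoint concerns QTc, and pulse and blood pressure are analysed too. The protocol's account of the Phase 1 study reports detectable plasma drug in only two of the 63 patients measured. The documents therefore give no reason to treat QTc as a leading question.

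It is also fair to say that a change score would not isolate a drug effect. There is no control arm, and baseline is usually one tracing, up to 8 weeks before dosing and also used for selection. Concomitant drugs, time and regression to the mean would all contribute. Nor would pairing recover subjects without a Week 12 ECG. These points limit what the added analysis can prove. They do not justify leaving ECGs as the one safety domain here with no baseline-relative summary.

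**Conclusion.** The concern holds as a gap in safety reporting. The planned QTcF count does not distinguish limits newly exceeded after dosing from values already present at entry, and an individual rise that stays below the limit appears only in the listing. That conclusion rests on the text alone.

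The size is uncertain. The 0.1% to 12.7% of men starting above 450 msec depends wholly on assumed means, SDs and a normal shape, and could be negligible. The QTcB route affects only subjects with a slow heart rate admitted near the limit, and their number cannot be estimated from the documents.

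The documents do not support saying that a drug effect would be invisible, or that change from baseline would establish one. Efficacy analyses, sample size and power are unaffected. This is a minor improvement.

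**What to change.** In SAP 5.3.4 and Table 14.3.6:

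1. Add paired QTcF change from baseline at Week 12 and at Post-Treatment, with the number of pairs at each. Keep Post-Treatment as its own visit instead of windowing it into maintenance months.
2. Add counts of pre-specified increases, for example more than 30 and more than 60 msec. These values are illustrations and are not in the documents, so the sponsor should choose and justify the categories.
3. Report the 450 and 470 msec counts at baseline. Report separately the subjects newly above their limit, with those at or below it at baseline and with a later ECG as denominator.
4. Add a baseline-to-worst shift table, as is already planned for laboratory toxicities.
5. State that baseline is the last pre-dose Screening ECG, usually a single tracing, and footnote where an average of three was used.

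The cost is a few sentences and one more table from data already collected. The drawback is a noisier change score, open to regression to the mean, because baseline is usually one tracing while later values average three.
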